6.2.4 Definitions of dose limiting toxicities (DLTs)

A dose-limiting toxicity (DLT) is defined as an adverse event or abnormal laboratory value of CTCAE Grade ≥ 3 assessed as unrelated to disease, disease progression, inter-current illness, or concomitant medications that occurs within the first two cycles of treatment with the combination treatment and meets any of the criteria included in [Table 6-3](#).

Emerging data from the new field of immune-immune combination studies suggest that some immune-related adverse events have a prolonged latency ([Wolchok 2013](#)). As such, the DLT window for the combination cohort in this trial is extended to the length of two cycles or 42 days.

National Cancer Institute Common Terminology Criteria for Adverse events (NCI CTCAE) version 4.03 will be used for all grading. For the purpose of dose-escalation decisions, DLTs will be considered and included in the BLRM.

The investigator must notify the Sponsor immediately of any unexpected CTCAE Grade ≥ 3 adverse events or laboratory abnormalities. Prior to enrolling patients into a higher dose level, CTCAE Grade ≥ 2 adverse events will be reviewed for all patients at the current dose level.

DLTs include any adverse event of CTCAE Grade 3 or higher occurring in the first two cycles of treatment during the Phase Ib dose escalation part of the study, for which relationship to study treatment cannot be ruled, with the exceptions defined in [Table 6-3](#).

Table 6-3 Criteria for defining dose-limiting toxicities

For the purpose of dose escalation and cohort expansion, DLT will be defined as follows: Any Grade 4 AEs will be considered DLTs with the exception of:
Neutropenia lasting ≤ 5 days that is not associated with fever or other clinical symptoms.
Lymphopenia or leukopenia at any grade
Any Grade 3 AEs will be considered DLTs with the exception of:
Electrolyte abnormalities that are not associated with clinical sequelae and are corrected to \leq Gr1 with appropriate management or supplementation within 72 hours of onset.
Infusion reaction that resolves to \leq Grade 1 within 6 hours.
Nausea and vomiting persisting for < 2 days with optimal anti-emetic therapy.
Thrombocytopenia without significant bleeding.
Diarrhea persisting for < 2 days with optimal anti-diarrhea therapy.
Hypertension persisting < 7 days with optimal therapy.
Infection or fever in the absence of neutropenia persisting < 7 days.
Rash or photosensitivity persisting < 7 days after treatment.

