Grade 3	Hold study treatment. GI consultation. Upon resolution to \leq Grade 1 and tapering of steroid requirement to \leq 10 mg prednisone per day, consider resuming study treatment after discussion with the Novartis Medical Monitor.
Grade 4	Discontinue study treatment.

Toxicity	Dose Adjustment Rules*
Hepatic (AST and/or ALT elevation)	
Grade 2 AST and/or ALT	Hold study treatment. Manage per institutional practice. Upon resolution to \leq Grade 1 or baseline, consider resuming study treatment without dose modification.
Grade 2 transaminitis with bilirubin $>1.5 \times$ ULN (unless Gilbert's syndrome)	Discontinue study treatment.
Grade 3 AST and/or ALT	Hold study treatment. Manage per institutional practices. Upon resolution to \leq Grade 1 or baseline within 7 days, consider resuming study treatment without dose modification after discussion with the Novartis Medical Monitor. Otherwise, discontinue study treatment
Grade 4 AST and/or ALT	Discontinue study treatment.
Isolated total bilirubin elevation**	
Grade 2	Hold study treatment. Upon resolution to \leq Grade 1 or baseline, may continue study treatment without dose modification.
Grade 3	Hold study treatment. Upon resolution to \leq Grade 1 or baseline, may consider resuming study treatment after discussion with the Novartis Medical Monitor.
Grade 4	See footnote**. Otherwise, discontinue study treatment.
Asymptomatic amylase and/or lipase elevation***	
Grade 3 or Grade 4, not associated with symptoms or clinical manifestations of pancreatitis***	Continue study treatment. If levels do not resolve to \leq Grade 2 within \leq 14 days after the initial report, hold study treatment. Upon resolution to \leq Grade 2, may resume study treatment without dose modification, after discussion with the Novartis Medical Monitor.
Pancreatitis	
Grade 2 / radiologic evidence	Hold study treatment. Manage per institutional practice. Upon resolution to \leq Grade 1, may resume study treatment without dose modification, if no clinical evidence of pancreatitis and after discussion with the Novartis Medical Monitor.
Grade 3-4	Discontinue from treatment.
CK elevation	

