Grade 2 myocarditis, or Grade ≥ 3 other cardiac disorders related to study treatment	Discontinue study treatment
Musculoskeletal	
Grade 2 or Grade 3	Hold study treatment. Consider resuming study treatment without dose modification upon resolution to ≤ Grade 1 with appropriate management.
Grade 4	Discontinue study treatment. In some cases, resuming study treatment may be considered after discussion with the Novartis Medical Monitor and consultation with a rheumatologist.

Toxicity	Dose Adjustment Rules*
Neurology	
Grade 1	Consider study treatment hold, particularly for clinical suspicion of Guillain-Barre syndrome, encephalitis, aseptic meningitis, transverse myelitis, or peripheral neuropathy.
Grade 2	Hold study treatment. In some cases, resuming study treatment may be considered after discussion with the Novartis Medical Monitor.
Grade 3 or Grade 4	Discontinue study treatment.
Infusion Reaction	
Grade 1	Decrease infusion rate until recovery
Grade 2	Stop infusion. Before restarting - administer oral pre-medication (e.g. 1000 mg of acetaminophen/paracetamol, 50-100 mg diphenhydramine hydrochloride or alternative antihistamine), within 60 minutes of restarting the infusion. Restart infusion at 50% of previous rate under continuous observation. Ensure that there is a minimum observation period of 1 hour prior to restarting the infusion(s). If the AE recurs at the reinitiated slow rate of infusion, and despite oral pre-medication, then discontinue patient from treatment.
Grade 3 or 4	Discontinue infusion immediately, and discontinue study treatment. Provide supplemental oxygen, fluids, and other resuscitative measures as needed. Monitor vital signs (e.g. blood pressure, pulse, respiration, and temperature) every 15 ± 5 minutes until resolution.
Other laboratory adverse events, not specified elsewhere in table and not included in the consensus guidelines	
Grade 3	Hold study treatment. Upon resolution to ≤ Grade 1, resume study treatment without dose modification.
Grade 4	Isolated Grade 4 electrolyte abnormalities not associated with clinical sequelae and corrected after appropriate management within 72 hours of their onset do not require discontinuation. In the case of Grade 4 electrolyte imbalances associated with clinical sequelae, or not resolved to ≤ Grade 1 within 72 hours despite appropriate management, discontinue study treatment.
Other non-laboratory adverse events, not specified elsewhere in table and not included in the consensus guidelines	

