Grade 2	Consider study treatment hold, at Investigator discretion. Upon resolution to ≤ Grade 1, resume study treatment without dose modification.
Grade 3	Hold study treatment. Upon resolution to ≤ Grade 1, resuming study treatment must be discussed with the Novartis Medical Monitor.
Grade 4	Discontinue from treatment.
*Delay: treatment may be delayed for 7 days due to AEs. If a scheduled dose of ongoing study drugs is delayed longer than 7 days due to an unresolved AE, the administration should be skipped and treatment resumed at a lower dose level (if meeting the criteria for DLT) at the next scheduled dose (Section 6.1.1). Treatment: refers to both study drugs, unless one has been discontinued.	

Toxicity	Dose Adjustment Rules*
**Note: If Grade 3 or 4 hyper-bilirubinemia is due to the indirect (non-conjugated) component only, and hemolysis as the etiology has been ruled out as per institutional guidelines (e.g., review of peripheral blood smear and haptoglobin determination), then delay study treatment until resolved \leq Grade 1, and resume study treatment at the discretion of the investigator.	
***Note: A CT scan or other imaging study to assess the pancreas, liver, and gallbladder must be performed within one week of the first occurrence of any \geq Grade 3 of amylase and/or lipase.	

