7.2.2.5 Laboratory evaluations

Abnormal laboratory values that are clinically significant (e.g., require an interruption or delay of study treatment, lead to clinical symptoms, or require therapeutic intervention) must be documented in the Adverse Event eCRF.

Novartis will be provided with a copy of the site’s local laboratory certification and tabulation of the normal ranges for each parameter required at study start and should be kept up to date on an ongoing basis. In addition, if at any time a patient has laboratory parameters obtained from a different outside laboratory, Novartis must be provided with a copy of the certification and a tabulation of the normal ranges for that laboratory.

Table 7-4 Local/Central Clinical laboratory parameters collection plan

Test Category	Test Name
Hematology	Hematocrit, Hemoglobin, Platelets, White blood cells with differential (neutrophils, lymphocytes, monocytes, basophils, eosinophils,)
Chemistry	Albumin, Alkaline phosphatase, ALT (SGPT), AST (SGOT), Bicarbonate, Calcium, Phosphate, Chloride, Magnesium, Creatinine, Glucose (non fasting), Creatine kinase, Lactate dehydrogenase (LDH), Total Bilirubin (also measure direct and indirect bilirubin if total bilirubin is > Grade 1), Blood Urea Nitrogen (BUN) or Urea, Uric Acid. CK-MB isoenzyme, Troponin I/T, Aldolase or Myoglobin or other skeletal muscle marker- if required per local guidelines to rule out myositis/rhabdomyolysis (see Section 7.2.2.6.2)
Cytokines *	IFN-γ, IL-6, IL-1, TNF-α
Urinalysis	Macroscopic panel (Dipstick) (Bilirubin, Blood, Glucose, Ketones, White blood cells, pH, Protein, Specific Gravity) Myoglobin-if required to rule out myositis/rhabdomyolysis per local guidelines
Coagulation	Prothrombin time (PT) or International normalized ratio [INR]), Partial thromboplastin time (PTT), Activated partial thromboplastin time (APTT)
Thyroid	T3 [free], T4 [free], TSH
Virology	HBV and HCV
*To be performed by a Central Laboratory	

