7.2.2.5.2 Clinical chemistry

Clinical chemistry panel outlined in [Table 7-4](#) will be performed as per the assessment schedule in [Table 7-1](#).

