2.8.3 Laboratory data

Laboratory data will be converted into SI units and classified (by Novartis Oncology Statistical Programming) into CTC grades according to CTCAE v4.03 as applicable. Grade 5 will not be used.

Baseline comparisons will be done based on shift tables but not considered for derivation of CTC grade.

Laboratory data for which a CTC grading does not exist will be classified into low, normal, or high based on local laboratory normal ranges as applicable.

The following summaries will be produced for hematology and coagulation, biochemistry, urinalysis parameters:

- For parameters with CTC grades: Shifts from baseline to the worst post-baseline CTC grade,
- For parameters with no CTC grades defined: Shifts from baseline to the worst post-baseline using low/normal/high classifications.

The following listings will be produced:

- Listing of all laboratory data with values flagged to show corresponding CTC grades and the classifications relative to the laboratory reference ranges (i.e., High (H) or Low (L)).

Both fasting glucose and non-fasting glucose will be summarized and listed for information integrity. Both of glucoses will be combined and reported based on CTCAE v4.03. Fasting glucose values will be flagged in the listing.

Table 2-1 and Table 2-2 lists all laboratory parameters that will be summarized.

Table 2-1 Laboratory parameters for which CTCAE grades are defined

Hematology and coagulation		Biochemistry		Urinalysis
White Blood Cells (WBC)	↑↓	Creatinine	↑	Protein ↑
Hemoglobin	↓	Uric acid	↑	
Platelets	↓	Magnesium	↑↓	
Neutrophils(absolute or %)	↓	Calcium	↑↓	
Lymphocytes(absolute or %)	↑↓	Phosphate	↓	
Partial thromboplastin time (PTT)	↑	Albumin	↓	
Activated partial thromboplastin time (APTT)	↑	AST (SGOT)	↑	
International normalized ratio (INR)	↑	ALT (SGPT)	↑	
		Chloride	↓	
		Bicarbonate	↓	
		Total Bilirubin	↑	
		Glucose	↑↓	
		Alkaline Phosphatase	↑	
		Creatine kinase	↑	

↑ Indicates that CTC grade increases as the parameter increases.

↓ Indicates that CTC grade increases as the parameter decreases.

Table 2-2 Laboratory parameters (without CTCAE grades) for which lab reference ranges are defined

Hematology and coagulation	Biochemistry	Urinalysis
Prothrombin time (PT)	Blood Urea Nitrogen (BUN) or Urea	Specific gravity
Hematocrit	T3 [free]	Glucose
Basophils (absolute or %)	T4 [free]	Blood
Eosinophils(absolute or %)	TSH	Bilirubin
Monocytes(absolute or %)	Direct bilirubin	Ketones
	Indirect bilirubin	White Blood Cells

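### Table 7-4 schedules no amylase or lipase, so the Table 6-4 rule on asymptomatic elevation has no scheduled trigger; sodium and potassium are also missing, so the electrolyte rules are only partly covered

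*Protocol*

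**What the plan says.** **What is measured.** Protocol Section 7.2.2.5.2 calls for the "Clinical chemistry panel outlined in" Table 7-4, at the visits in Table 7-1. The Table 7-4 chemistry row starts "Albumin, Alkaline phosphatase, ALT (SGPT), AST (SGOT), Bicarbonate, Calcium, Phosphate, Chloride, Magnesium, Creatinine, Glucose (non fasting), Creatine kinase, Lactate dehydrogenase (LDH", adds total bilirubin, and ends with "Blood Urea Nitrogen (BUN) or Urea, Uric Acid. CK-MB isoenzyme, Troponin I/T, Aldolase or Myoglobin or other skeletal muscle marker". The muscle markers are conditional on local guidelines.

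**What the rules act on.**
- Table 6-4 (Section 6.3.1) has a row headed "Asymptomatic amylase and/or lipase elevation" for Grade 3 or 4 values without clinical pancreatitis. Treatment continues at first and is held if the value has not come down to Grade 2 or lower within 14 days of the initial report.
- The footnote to that row says "A CT scan or other imaging study to assess the pancreas, liver, and gallbladder must be performed within one week of the first occurrence" of a Grade 3 or higher value.
- Table 6-3 (Section 6.2.4) exempts from the Grade 3 DLT definition "Electrolyte abnormalities that are not associated with clinical sequelae and are corrected to" Grade 1 or lower within 72 hours of onset.
- Table 6-4 says that "Isolated Grade 4 electrolyte abnormalities not associated with clinical sequelae and corrected after appropriate management within 72 hours of their onset" do not require discontinuation; other Grade 4 electrolyte imbalances do.

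**What is analysed.** SAP Section 2.8.3 says that its Tables 2-1 and 2-2 give the complete set: "lists all laboratory parameters that will be summarized". None of the four analytes is there.

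**The concern.** An elevation without symptoms has no clinical sign to prompt a test, so a laboratory value has to reveal it. The protocol writes a management rule and a mandatory imaging step for such values but never asks for the measurement. Whether the rule is ever applied then depends on local testing habit.

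This matters because safety and tolerability are the primary Phase Ib objective and a secondary objective in Phase II. Table 6-3 has no amylase or lipase exception, so such an event falls under its general Grade 3 and Grade 4 provisions if a relationship to treatment cannot be ruled out. Under Section 8.1.2.1 an abnormality that needs a protocol-required hold is by definition an adverse event. A persistent elevation within the 42-day window could therefore count as a DLT in the dose-escalation model, but only at a site that chose to test. Section 10.1.4 in turn lets patients count as DLT-free when the sponsor and investigators judge the safety data sufficient, and these analytes were never part of the required data.

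**Working it through.** No sample size, power or error rate is involved. The check compares the list of analytes collected with the list that the rules need.

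| Analyte | Protocol Table 7-4 | SAP Tables 2-1/2-2 | Rule that uses it |
|---|---|---|---|
| Amylase | no | no | Table 6-4 row and imaging footnote |
| Lipase | no | no | Table 6-4 row and imaging footnote |
| Sodium | no | no | Electrolyte rules, Tables 6-3 and 6-4 |
| Potassium | no | no | Electrolyte rules, Tables 6-3 and 6-4 |
| Calcium, magnesium, phosphate, chloride, bicarbonate | yes (all five) | yes (all five) | Electrolyte rules, Tables 6-3 and 6-4 |

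**Amylase/lipase rule.** 0 of 2 trigger analytes are scheduled. No baseline value is required either.

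**Electrolyte rules.** Neither rule names an electrolyte. If the relevant set is taken as the five on the panel plus sodium and potassium (an assumption, since the documents do not define it), 5 of 7 are covered.

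**Visits affected.** Table 7-1 schedules chemistry at screening; Cycle 1 Days 1, 8 and 15; Cycle 2 Days 1 and 15; Cycle 3 Day 1; Cycle 4 Days 1 and 8; Day 1 of later cycles; and end of treatment. With 21-day cycles, Cycle 2 Days 1 and 15 are study days 1 + 21 = 22 and 15 + 21 = 36, and Cycle 3 Day 1 is study day 1 + 42 = 43. The 42-day DLT window thus contains five chemistry visits (study days 1, 8, 15, 22 and 36). None includes any of the four analytes.

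**Could this be a reading artefact?** It is unlikely. Table 7-4 shows no redaction, and the SAP tables omit the same four.

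**Could the tests be required elsewhere?** No other section schedules them. Table 7-4 does carry conditional tests where these were intended (the muscle markers), but does not list amylase or lipase even on that basis.

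**The case against.** The best defence is that a dose-modification table says what to do when an event comes to light and does not by itself create a duty to screen. Section 8.1.1 accepts adverse events found through any laboratory test, Section 7.2.2.5 provides for results from outside laboratories, and pancreatitis with radiologic evidence has its own row in Table 6-4. Routine enzyme testing would also lead to holds and imaging in patients without symptoms, and whether that is wanted is a clinical choice. This stands in part. The rule is not inoperable, because an unscheduled local test can trigger it. But the protocol does not say that the rule is meant for incidental findings only, and ascertainment is uneven as written.

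A reader might infer more than the documents support:
- **That the electrolyte rules do not work.** They do, for five scheduled electrolytes.
- **That Table 6-3 makes any electrolyte abnormality a DLT unless corrected in 72 hours.** The exception covers Grade 3 only and also requires no clinical sequelae.
- **That Table 6-3 names amylase or lipase.** It does not; only its general Grade 3 and 4 provisions apply.
- **That the laboratory tables would print a misleading zero.** The SAP has no row for these analytes, so no zero would appear there. Any reported event would go into the adverse event tables.
- **That the dose-escalation result is biased.** Nothing in the documents allows an effect on the model or on dose holds to be quantified.

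Timing also limits the remedy. According to the study status in Amendment 05, the last patient was enrolled on 10-Jan-2019 and 6 patients were on treatment on 08-Jul-2019. Baselines and DLT windows cannot be recovered.

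**Conclusion.** The point holds as a mismatch between the rules and the schedule. For amylase and lipase the gap is complete: a rule for patients without symptoms, and a mandatory imaging step, rest on two tests that the protocol never schedules and for which it requires no baseline. For electrolytes the gap is partial and confined to sodium and potassium.

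The consequence is one of ascertainment. The absence of reported amylase, lipase, sodium or potassium abnormalities cannot be read as absence of the abnormality, and DLT-free status says nothing systematic about them. The population gives some reason to be careful: 20 of the 81 treated Phase II patients were in the pancreatic group. Whether any had raised enzymes before dosing is unknown from the documents and is not assumed here.

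The conclusion rests on Table 7-4 being the full required panel, as Section 7.2.2.5.2 indicates, and on the electrolyte rules including sodium and potassium, which they neither name nor exclude. It does not call the chosen dose or the efficacy results into question.

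**What to change.** 1. **Reconcile the documents.** Table 7-4 and SAP Tables 2-1/2-2 must agree with Tables 6-3 and 6-4 on which analytes the rules act on and which are collected. One route that leaves every threshold and dose rule unchanged is to list the four analytes in the existing chemistry panel. Whether routine testing is intended is for the sponsor's clinical team to state. With few patients left on treatment the yield for this trial is small; the main gain is for any later protocol that reuses the text.
2. **Disclose the gap for data already collected.** State in the SAP and clinical study report that amylase, lipase, sodium and potassium were not systematically measured. List any local values reported. Draw no incidence or DLT-free inference for these analytes.

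The first step costs four local assays on blood already drawn, plus short edits to the protocol and SAP tables, with no new visit. The second costs a few sentences and, where values exist, one listing.

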7.2.2.5.1 Hematology

Hematology panel outlined in [Table 7-4](#) will be performed as per the assessment schedule in [Table 7-1](#).

7.2.2.5.2 Clinical chemistry

Clinical chemistry panel outlined in [Table 7-4](#) will be performed as per the assessment schedule in [Table 7-1](#).

7.2.2.5.3 Urine analysis

Urine analysis panel outlined in [Table 7-4](#) will be performed as per the assessment schedule in [Table 7-1](#).

7.2.2.5.4 Thyroid function

Thyroid function panel outlined in [Table 7-4](#) will be performed as per the assessment schedule in [Table 7-1](#).

7.2.2.5.5 Cytokines

Samples for the cytokine panel outlined in [Table 7-4](#) will be collected at the following time points:

- Baseline (predose C1D1)
- On an *ad-hoc* basis, in case a patient has an adverse event suspected to be a cytokine release syndrome. In such case, this assessment should be performed at the following time points:
 - a. within 5 hours (or as soon as possible) after the occurrence of the adverse event
 - b. one week after the occurrence of the adverse event.

Samples for cytokine panel assessment will be stored locally below -70°C. The samples will be analyzed retrospectively in batches by the Novartis designated central laboratory. Immediate analysis of the samples by the central lab will be done only for patients who experienced an adverse event suspected to be a cytokine release syndrome and had follow-up samples collected.

7.2.2.5.6 Coagulation

Coagulation markers outlined in [Table 7-4](#) will be performed as per the assessment schedule in [Table 7-1](#).

7.2.2.5.7 Pregnancy

Pregnancy tests will be performed for women of child bearing potential per [Table 7-1](#).

At screening, a serum pregnancy test must be performed within 3 days before the first dose. During the study (Day 1 of each Cycle starting with Cycle 2), and at the End of Treatment visit, a serum pregnancy test must also be performed.

A urine pregnancy test should be performed every month during and at the end of the safety follow-up period (i.e. 150 days after the last dose of PDR001 or 90 days after the last dose of MCS110 for patients who stopped PDR001 and continued MCS110 alone for more than 60 days). If the patient is not coming to the clinic during the safety follow-up, it can be performed at home or at a local doctor's office, and the results will be communicated to the site staff. These follow-up pregnancy tests will be recorded only in the source documentation, not in the CRF.

